### **Recruitment Methods**

*Note: Attach all applicable recruitment materials to the last section of the Smart form under "Recruitment Materials."*

1. Which of the following methods will be used to recruit research participants. – *Select all that apply*

- Email
- Phone call
- Letter
- Advertisement (e.g., poster, flyer, etc.)
- Social media
- Other. *Please specify:*

2. Describe when, where, and how potential research participants will be recruited .

Page 5 of 29

*Study participants (who meet the study criteria) will be recruited through both public and private mental health agencies, counseling centers, support groups, community health centers, health fairs and other community events, print and e-newsletters (e.g. CASE Daily), local magazines and newspapers, the registry of bipolar persons used by CI [name] and other research registries of people with mental illness and/or their family caregivers approved for use from the investigators in the Department of Psychiatry, and private physician offices in Cuyahoga and 6 adjacent counties in Northeastern Ohio. We will post/distribute flyers describing the study and contact information in public venues; caregivers will contact the study office for further information and enrollment. In addition, agency personnel/health care professionals may nominate a caregiver for the study. If additional caregivers are needed, we will use snowball recruitment by asking study participants to refer others like them to the study. We will also recruit via the internet using social media sites (e.g. Twitter, Facebook, Instagram, and other online sources).*

3. Describe the source (e.g., from what department, EMR, etc.) of the research participants.

*Study participants will be recruited through both public and private mental health agencies, counseling centers, support groups, community health centers, health fairs and other community events, print and e-*

newsletters (e.g. CASE Daily), local magazines and newspapers, the registry of bipolar persons used by CI [name] and other research registries of people with mental illness and/or their family caregivers approved for use from the investigators in the Department of Psychiatry, and private physician offices in Cuyahoga and 6 adjacent counties in Northeastern Ohio.

4. Describe the methods that will be used to **identify** potential research participants.

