## Consent Process

**Indicate whether you will be obtaining consent:**

Yes  No

If yes, answer the following questions:

1. Describe where the consent process will take place:

*After eligibility is verified during phone screening by a team member, the consent form will be reviewed verbally and questions about the study will be answered. During the first appointment with the data collector, the consent form will be reviewed again and signed by both the study participant and data collector before beginning the data collection interview.*

Page 7 of 29

The time that will be devoted to the consent discussion:

*There are no time constraints to the consent discussion. The consent discussion will take place during the screening phone call and again at the enrollment meeting, prior to data collection.*

3. Any waiting period available between informing the prospective subject and obtaining the consent:

*Yes. After verifying eligibility and reviewing the consent form during the screening phone call, there is a period of time between the phone call and the enrollment meeting. The length of time between the two varies depending on the meeting time selected by the research participant and team member.*

4. Steps that will be taken to ensure the research participants' understanding:

*Study participants will have time to ask questions about the study and review the consent form before signing it.*

5. Any process to ensure ongoing consent:

*Within approximately one month of the first data collection session, the participants will be made aware of which of the four groups (control, usual care, SM-need, or SM-preference) that they have been randomly assigned to. Those who are randomly assigned to usual care, SM-need, or SM-preference will need a second-level consent, obtained at the beginning of the training session for that particular intervention. The second-level consent process is needed in order to keep the control group and usual care groups blinded to the content of the interventions being tested. Knowledge of the other interventions could motivate them to seek out similar strategies on their own and confound the study.*

6. Steps that will be taken to minimize the possibility of coercion or undue influence to the subjects:

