## **Study Design/Procedures**

**Directions: 1) Describe the overall study design. 2) Provide a description of all study-related research procedures being performed, including the length of time involved. 3) Include procedures being performed to monitor research participants for safety or minimize risks. 4) Describe the source records including medical or educational records, which will be used to collect data about subjects.**

*The study is a four-year randomized controlled trial in Northeastern Ohio and includes a convenience sample of family caregivers of adults with bipolar disorder. After eligibility is verified during phone screening by team member, the consent forms will be reviewed verbally, questions about the study will be answered, and the study enrollment/first data collection appointment will be made.*

*There are three structured data collection time points (T1/enrollment, T2/ 6months after initiation of intervention, T3/ 12 months after initiation of intervention); these will be face-to-face with a research assistant, using a desktop, laptop, or iPad with secure REDCap software. During the enrollment and first data collection meeting, we will obtain informed consent from the caregiver. Caregivers will have time to ask questions about the study and review the consent form before signing it.*

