Individuals will be assigned a study ID using our enrollment log. In addition, at enrollment we will collect demographic information including age, gender, race, ethnicity, marital status, education, income, occupation, hours of work/week, if the participant is an employee or student at CWRU, health conditions, current medications, relation to person with bipolar, age of family member with bipolar, how many years ago was family member diagnosed with bipolar disorder, specific diagnosis of family member, predominant behavior style of family member with bipolar, whether or not caregiver lives with this family member, whether or not caregiver provides care/assists with basic needs (and how many hrs/day), how many years caregiver has been providing care, if other adults help provide care for family member with bipolar disorder. Some, but not all of the demographic and other questions asked at baseline will also be asked at T2 and T3. We will then proceed with data collection, consisting of surveys to measure bipolar symptoms, caregiver reactions, caregiving involvement, bipolar knowledge, resourcefulness, health risks, and health outcomes. They will also have their heart rate variability (HRV) measured using a non-invasive device on the wrists; it

will take approximately 10 minutes to collect the data. The entire first meeting will take approximately 60-90 minutes. The second and third data collection meeting will be approximately 60 minutes. In the event there is an equipment malfunction or a poor reading is obtained by a research team member, we may need to re-collect the HRV and/or survey data again after a data collection meeting. **COVID-19 modification:** HRV data will not be collected when data collection is done remotely (T2 or T3 only) and will be considered missing data. When we are able to collect HRV data, we will do so by bringing an HRV device to the study participant at a set date and time, providing instructions on how to use the HRV device, safety information on the HRV device, and also providing support via phone or video. HRV data collected this way will be collected for 15-20 minutes instead of 10 minutes, to ensure reliable data is collected. A study team member will collect the HRV device the same day or within 28 hours, at a mutually convenient time. Each HRV device will be sanitized before and after each study participants' use.

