*Individuals will be encouraged to continue with the interventions if they found them helpful (for BF, caregivers will have been given information on deep-breathing techniques without using a device). Caregivers who cannot be reached by phone or email for follow-up (either intervention or data collection) will have a letter sent to them if they have consented to having a letter sent to their home. Occasionally, calls will need to be made to study participants outside of the office (e.g., evenings/ weekends; when a research team member is working remotely/ in the field) or participants will request to be contacted by text. In these instances, the research team will use Google Voice, which allows users (research team) to set up a phone number through their CWRU email and is connected to their personal mobile phones. Calls and texts can be made to/ from the mobile phones while masking the actual phone number. When the research team is not working, calls will be directed to voicemail.*

*From Modification #8 (approved 03/06/2019)-- At the end of the T3 data collection, study participants will receive a brochure from each of the three interventions being researched, as well as an answer sheet for Caregiver Knowledge of Bipolar Disorder Questionnaire. Study participants who received an intervention will be asked a series of questions (up to 16) about their experience with, and opinion of, the intervention they received. Study participants who have already completed all three data collection sessions and have already agreed to be contacted for any questionnaire follow-up will be called and asked questions over the phone.*

Page 14 of 29

*The supplemental analysis will use baseline data (T1) to explore relationships among caregiver characteristics (race and gender), psychological stress (caregiver reactions and caregiving involvement), and physiological stress (heart rate variability time and frequency domains). De-identified baseline data from the demographic measures, psychosocial measures (caregiver reactions, caregiver involvement) and the HRV measurements will be used for this analysis.*

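### Handing out all three intervention brochures and the knowledge-test answer sheet at each caregiver's own T3 adds an unmanaged contamination risk while others are still in the trial

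*Combined protocol and SAP*

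**What the plan says.** **Concealment.** Consent Process, item 5, requires a further consent from everyone assigned to usual care, SM-need or SM-preference. Its purpose is to "keep the control group and usual care groups blinded to the content of the interventions being tested". The reason given is: "Knowledge of the other interventions could motivate them to seek out similar strategies on their own and confound the study".

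**Handout.** Study Design/Procedures sets the last assessment at "T3/ 12 months after initiation of intervention". The Modification #8 paragraph, approved 03/06/2019, adds: "At the end of the T3 data collection, study participants will receive a brochure from each of the three interventions being researched". The same handout includes the "answer sheet for Caregiver Knowledge of Bipolar Disorder Questionnaire". No arm is excepted. Nothing delays release until the last caregiver has finished, and nothing asks recipients not to pass the material on. Elsewhere in that section, control caregivers are promised access to the three interventions when the study ends. The text does not say whether that means their own T3 or closure of the trial.

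**Use of the knowledge score.** In the SM-need arm, a T1 knowledge score below 70% is the example rule for assignment to bipolar education.

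**Re-collection.** After an equipment fault or a poor reading, "we may need to re-collect the HRV and/or survey data again after a data collection meeting". T3 is not excluded.

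**Recruitment.** Recruitment Methods, item 2, draws caregivers from support groups, agencies and similar venues in seven counties. Only if more caregivers are needed, "we will use snowball recruitment by asking study participants to refer others like them to the study".

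**The concern.** The protocol itself treats knowledge of intervention content as a possible confounder and spends a second consent step on preventing it. The T3 handout puts all of that content, plus the key to a study questionnaire, into the hands of finishers who may know other caregivers in the trial.

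Two things are at stake:

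- **Contrast between arms.** A control or usual-care caregiver who obtains resourcefulness or breathing material before T2 or T3 may take up similar strategies. That would pull the arms together on the A1 health outcomes.
- **The knowledge score.** Anyone who sees the key before T1 could score above 70% without the underlying knowledge and, in SM-need, be put in the wrong need category. A key seen before T2 or T3, or before a repeated T3 survey, would bias those scores upward.

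**Working it through.** The plan states no leak rate, effect size or power, so there is no figure of its own to reproduce. The check is a comparison of passages, some date arithmetic and one illustration.

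**1. Do finishers overlap with active caregivers?**

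- By 03/06/2019 some caregivers had completed all three sessions (Modification #8), so T3 sessions were already being held.
- The COVID-19 Modifications text has T2 and T3 sessions still to come from April 2020.
- A T2 on schedule in April 2020 implies an intervention start 6 months earlier, in October 2019. Assignment is disclosed within about one month of T1, so T1 falls around September 2019. For a control caregiver, T2 is counted from enrolment (Research Participant Compensation), so T1 falls around October 2019.
- These T1 dates are 6 to 7 months after the handout was approved.
- The T3 matching an April 2020 T2 falls in October 2020. From March 2019 that gives up to about 19 months in which finishers could hold material while others were being followed.

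Overlap in follow-up is therefore clear. Overlap with enrolment is probable rather than certain, because it assumes that T2 visits ran roughly on time. For those April 2020 T2 caregivers all to have had T1 before March 2019, their T2 visits would have to be about 6 to 7 months late.

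**2. By what routes could the material reach someone whose data are still to come?**

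| Route | Person affected | Needs sharing? | Barrier in the plan |
|---|---|---|---|
| Shared support group or agency | Control or usual-care caregiver before T2 or T3 | Yes | None for this route |
| Referral by a participant, if used | Future enrollee before T1 | Yes | None for this route |
| Relative | Future enrollee | Yes | Exclusion 3, same household only |
| Re-collected T3 survey | The finisher | No | None stated |

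Under the COVID-19 text, some T2 and T3 surveys may be emailed for self-completion. Use of a key in that setting would not be observed.

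**3. How sensitive is a comparison to leakage? (illustration only)**

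Assumptions, none of them from the plan except the total of 360: equal arms, 360 / 4 = 90 each; two-sided 5%; true difference d = 0.40 SD; a share c of control caregivers gains the full intervention effect, so the contrast becomes d(1 − c).

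Power ≈ Φ[d(1 − c) × √(90/2) − 1.960], with √45 = 6.708.

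| c | d(1 − c) | × 6.708 | − 1.960 | Power |
|---|---|---|---|---|
| 0 | 0.40 | 2.683 | 0.723 | 76.5% |
| 10% | 0.36 | 2.415 | 0.455 | 67.5% |
| 20% | 0.32 | 2.147 | 0.187 | 57.4% |

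Starting instead from 80% power (d = 0.418), leakage of 2%, 5%, 10% and 20% gives 78.4%, 75.9%, 71.3% and 61.1%. At a few per cent the loss is small.

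**The case against.** The case on the other side is substantial.

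- **The recipient is past the last assessment.** Concealment serves caregivers during their own participation, and the handout follows T3. This stands, except for a re-collected T3 survey.
- **Sharing is not shown.** The documents show that it is possible, not that it occurs. Exclusion 3 gives partial protection, participant names are not disclosed to one another, recruitment is spread widely, and referral is conditional. All of this stands.
- **Content already circulates.** SM-preference caregivers choose among the three interventions before T2, and every trained caregiver keeps print material. This stands, but that print material covers the caregiver's own intervention. The T3 handout is the only described release of all three together, and of the answer sheet.
- **Earlier finishers may not hold the material.** For those who had completed all sessions before Modification #8, the text specifies only a telephone interview. This stands, so the overlap is counted from the modification onward.
- **Knowledge is not an A1 outcome.** A1 concerns health risks and physical and mental health. The Data Analysis Plan specifies no test of T2 or T3 knowledge, and A3 examines its cut points descriptively. This stands.
- **A second-hand brochure is not the intervention.** It lacks the training session, the 28-day journal, the weekly follow-up and, for biofeedback, the device. Usual care already receives education. The power figures also describe one pairwise contrast, not the planned 4 × 3 repeated-measures analysis. This stands, so they are upper bounds.
- **Delay has a cost.** Untreated control caregivers who finish early could wait more than a year for brochures. This is a fair reason to leave brochure timing to the investigators.

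**Conclusion.** The T3 handout leaves an unmanaged contamination risk to a concealment that the protocol calls necessary, and the sections on consent, control-arm access and the T3 handout are not reconciled. The answer sheet is the stronger half of the point: it is the key to an instrument still in use, its T1 score helps determine assignment within SM-need, and nothing else in the plan releases it. The brochures are the weaker half.

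A reader might infer that the handout defeats the concealment, or that T2 and T3 knowledge scores become uninterpretable. The documents support neither. Recipients' own data are normally complete, harm otherwise depends on sharing at an unknown rate, and knowledge scores would at most be biased in those exposed. A reader might also take the fall from 77% to 57% as an expected loss; it follows only from assuming that 20% of controls gain the full effect.

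The effect on T1 assignment rests on enrolment having continued after March 2019, which the dates make probable. The current version (6.2, latest date 3/11/2021) mentions remaining T2 and T3 sessions but no remaining T1, so a change at that stage may protect only follow-up data. This is a low-cost improvement of uncertain benefit, not evidence of a compromised trial.

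**What to change.** 1. **Answer sheet** (Study Design/Procedures, Modification #8): withhold it until after the last T3 in the trial. Send it with the one-page results summary already planned under Sharing of Results with Research Participants.
2. **Brochures:** ask finishers not to share them with other caregivers until the trial closes. Delaying the brochures themselves is optional, because early finishers, including untreated controls, would then wait longer.
3. **Re-collection** (Study Design/Procedures): allow no repeat of a T3 survey once any material has been given. Check that the survey data are complete before the handout.
4. **Wording:** state whether control caregivers' access to the interventions begins at their own T3 or at trial closure, and bring that into line with the Modification #8 paragraph and Consent Process, item 5.

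Cost: a short amendment, one sentence in the T3 script and an enclosure in a mailing already planned. The downside is that finishers wait longer for the answer sheet, and that a faulty T3 survey found after the handout would stay missing.

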### **Study Timeline (optional)**

### **ClinicalTrials.gov Information**

**Directions:** If this study has been registered on ClinicalTrials.gov, provide the ClinicalTrials.gov identifier and the investigator/sponsor responsible for registering. If this study has not been registered on ClinicalTrials.gov, provide the rationale as to why and if/when it will be. If it does not meet the requirement for being registered on ClinicalTrials.gov, please state that.

NCT03023332

### **List of Data to be Collected**

• *Indicate what identifiers you will collect*

- Name
- Address (e.g., Zip code, other geographical designation, etc.)
- Dates related to an individual (e.g., Date of admission, birth, surgery, etc.)
- Telephone number
- Fax number
- Email address
- Social security number
- Medical record number
- Health plan beneficiary number
- Account number
- Certificate/license number
- Any vehicle or other device serial

Page 15 of 29

- Device identifiers or serial numbers
- Web URL
- Internet protocol (IP) address
- Finger or voice prints (*includes audio recordings*)
- Photographic images (*includes video recordings*)
- Other: Any characteristic that would uniquely identify the individual

If other, please explain:

*Heart rate variability requires non-invasive electrocardiography*

1. List all other data to be collected for the research study. Attach all data collection tools on the Local Site Documents page of the SpartaIRB smart form (Other Attachments).

- *Questionnaires to measure bipolar symptoms, caregiver reactions, caregiving involvement, bipolar knowledge, resourcefulness, health risks, and health outcomes. (Listed under site related documents as 'questionnaires.pdf')*
- *Intervention evaluation questionnaire*

*(Listed under site related documents as 'script intervention eval questionnaire.pdf')*

- *Intervention journals*

*(Listed under site related documents as 'resourcefulness sample journal page.pdf', 'biofeedback sample journal page.pdf', 'bipolar education sample journal page.pdf')*

- *COVID-19 questions at remaining data collection sessions (consent included with questionnaire)*

## **Data Analysis Plan**

**Directions: Describe the data analysis plan, including any statistical procedures. If applicable, provide a power analysis, and study/safety endpoints.**

*The primary aim (A1) is to examine differences across four groups of family caregivers on caregiver health over time. The underlying analyses for A1 are built around the repeated measures analysis of variance (RMANOVA). The primary analysis will be a set of 4 group X 3 time waves RMANOVA. These analyses will compare the four groups: 1) a control group (no intervention); 2) education (usual care); 3) SM-need; or 4) SM-preference across three time waves of health risks and physical and mental health outcomes. When using RMANOVA, one not only assesses mean differences across time, but also assesses group differences and the interaction of time X group, which allow us to test the trend of the means over time across the four groups.*

*The RMANOVA, not only can be used to determine if there are mean differences across the three time periods, it can utilize orthogonal polynomial contrasts to determine if there are mean and quadratic trends of the means across time. Orthogonal polynomials are weights assigned to each time period that model a linear or quadratic non-linear trend. RMANOVA can determine if these trends in the mean are significant. A linear trend is indicated if there is a change in direction based on scores across the time waves. The major assumption to be tested with RMANOVA is sphericity. Sphericity is a form of compound symmetry and refers to the equality of variances of the differences between time waves. If the assumption of sphericity is violated based on the Mauchly's test, SPSS provides and adjusted F, df, and P-value in RMANOVA to account for the violation.*

*Secondary aims are to: A2) explore whether caregiver need or their preference for interventions associated with: a) care recipient's symptoms; b) caregiver reactions; and c)*

caregiving involvement; and **A3**) build caregiver profiles from demographic/contextual factors that are associated with their needs and preferences for the self-management interventions. Accordingly, **A2** will be tested with a series of bivariate analyses including correlations, one way analyses of variance (ANOVA) and independent samples t-tests. We will run correlations when both variables are continuous. If the independent predictor variable is categorical and the dependent outcome is continuous, we will run an ANOVA. When the independent variable is dichotomous and the outcome is continuous, an independent samples t-test will be run. **A3** will build profiles 8 groups from two of the study arms: 1) SM-need and 2) SM-preference. To identify the unique characteristics of each group. Univariate descriptive statistics will be run on the contextual variables within the caregiver, care recipient, and caregiving situation. We will also examine cut points from measures of the self-management processes (knowledge, resourcefulness, and heart rate variability). These analyses will build profiles to show which caregivers may benefit most from a specific self-management intervention. We will prescreen for potential violations of assumptions for correlations. Scatter plots between two variables will identify influential cases, patterns of nonlinearity and constant-error variance that may reduce Parson's  $r$ . To address potential violation of the assumptions, influential cases can be removed. Data transformations can be used to remedy issues such as non-linearity, non-constant error variance, and non-normal error variance. For ANOVAs and t-tests, assumptions of normality and homogeneity of variance will be tested. Non-parametric equivalence tests will be used if assumptions are violated.

For the supplemental analysis, VivoSense software will be used to perform automatic cleaning and computation of heart rate variability measures (SDNN, RMSSD, TP, VLF, LF, HF, LF/HF). Data analysis will consist of descriptive and inferential statistics using SPSS. Description of the sample will include age, gender, race/ethnicity, marital status, education level, annual income, and caregiver relationship. Additionally, descriptive statistics will be calculated for the study measures.

The aims for the supplemental analysis are to: **SA1**) determine whether there are differences by caregiver characteristics (race and gender) on measures of psychological stress responses (caregiving involvement and caregiver reactions), **SA2**) determine whether there are differences by caregiver characteristics (race and gender) on measures of physiological stress responses (heart rate variability domains), **SA3**) examine associations among indicators of psychological stress responses (caregiver reactions and caregiving involvement) and physiological stress responses (heart rate variability domains, and **SA4**) explore relationships among time and frequency domains of heart rate variability. **SA1** and **SA2** will be tested with a series of independent samples t-tests. **SA3** and **SA4** will be tested with a series of bivariate correlations.

Potential violations of assumptions for correlations and t-test will be assessed. To address violations of the assumptions for correlation, influential cases may be removed. Data transformations may be used to remedy issues such as non-linearity, non-constant error variance, and non-normal error variance. To address violations of the assumptions for t-test, non-parametric equivalence tests will be used if assumptions are violated.

